7.2 Protocol Violations and Deviations

Protocol deviations will be collected by the clinical team and provided to Premier biostatistics prior to database lock. Deviations will be reviewed on a case-by-case basis to be classified as major or minor by the project team prior to database lock. Major and minor deviations will be included in a listing.

7.3 Demographics and Other Baseline Characteristics

Descriptive summaries and frequencies/percentages of demographic and other baseline characteristics will be completed for all enrolled subjects in the safety population for data collected in HZNP-ACT-301. These tabulations will include the following variables:

- Demographics (age, age categories (10-16 inclusive, and 17 and above), gender, race, ethnicity, height, weight, and Body Surface Area (BSA))

Tabulations of baseline HZNP-ACT-301 efficacy assessments will include the following in a separate table:

- FA Functional Stage
- FARS-mNeuro score
- ADL
- T25FW
- FARStot

Descriptive summaries and frequencies/percentages of demographic and other baseline conditions in separate tabulations will include the following:

- Medical History
- Prior Medications
- Baseline Physical Examination

Medical History: Incidences of findings in medical history will be summarized by System Organ Class and preferred term.

Prior Medications: The frequency and percentage of all prior medications will be summarized by Anatomical Therapeutic Chemical (ATC) classifications level 3 and preferred term for all subjects. Subjects will only be counted once within ATC and preferred term. These data will be grouped by overall treatment.

Baseline physical examination: Baseline physical examination will be summarized by body system and result by overall treatment.

8. EFFICACY ANALYSIS

All analyses are being conducted for an abbreviated safety CSR, and no efficacy analysis will be carried out.

9. SAFETY AND TOLERABILITY ANALYSIS

The analysis of safety assessments in this study will include summaries of the following categories of safety and tolerability data collected for each subject:

- Adverse Events
 - Summary of all Adverse Events
 - TEAEs, and Serious Adverse Events (SAEs)
 - TEAEs by severity
 - TEAEs by relationship to study drug
 - TEAEs leading to premature withdrawal
 - Any deaths
- Clinical Laboratory Investigations
 - Complete Blood Count
 - PT, INR, and aPTT
 - Chemistry panel
 - Urinalysis
 - Immunogenicity samples
- Electrocardiograms (ECG)
- Echocardiograms
- Physical Examinations
- Concomitant Medications

- Study Drug Exposure and Treatment Compliance

All tabulations and summaries for these categories will be performed on the safety population unless otherwise noted.

9.1 Adverse Events

Missing and partially missing AE start and/or stop dates will be imputed for the purpose of statistical analysis, according to the specifications described in Section 6.1.

A summary of overall TEAEs, TEAEs, SAEs, TEAEs leading to PW, TEAEs by relationship to study drug, and severity of TEAEs will be presented by overall treatment.

Summaries and incidence rates (frequencies and percentages) of individual TEAEs by MedDRA System Organ Class (SOC) and preferred term will be displayed by overall treatment received. Such summaries will be displayed for TEAEs, SAEs, TEAEs leading to early termination, TEAEs by relationship to study drug, and TEAEs by severity

Each subject will be counted only once within each preferred term. If a subject experiences more than one TEAE within a preferred term only the TEAE with the strongest relationship or the maximum intensity, as appropriate, will be included in the summaries of relationship and intensity. No inferential statistical tests will be performed.

In the AE data listings, all AEs will be displayed. AEs that are not treatment-emergent will be flagged.

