While the approved ACTIMMUNE dose regimen does not involve initial dose escalation or titration, a recently completed study in healthy volunteers demonstrated a potential reduction in the severity of acute FLS when dose escalation to the standard dose was utilized [[Devane et al, 2014](#)]. This mirrors the clinical experience with other IFNs, particularly the interferon-betas (IFN- β s) used by multiple sclerosis patients where initial dose escalation using an acute titration regimen has been adopted. Natural tolerance to FLS develops relatively quickly in the majority of patients receiving IFNs and the dose escalation/titration minimizes the initial poor tolerability and treatment dropouts. It is expected that the use of the acute dose escalation as proposed in this protocol will facilitate subject retention during the early phase in the trial, particularly with dose escalation to 100 µg/m².

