8. STUDY OBJECTIVES

8.1 Primary Study Objective

The primary objective is to evaluate the long-term safety of ACTIMMUNE (IFN- γ 1b) in subjects with FA.

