In order to maintain the study blind in HZNP-ACT-301, all subjects in this open-label extension study will undergo ACTIMMUNE titration, regardless if they received ACTIMMUNE or placebo in HZNP-ACT-301. The doses planned for dose escalation of ACTIMMUNE in this study are 10, 25, 50, and 100 $\mu\text{g}/\text{m}^2$. The approved dosage of ACTIMMUNE for the treatment of CGD and SMO is 50 $\mu\text{g}/\text{m}^2$ for patients whose BSA is greater than 0.5 m^2 and the highest dose administered in the OLIGA-FA pilot study was also 50 $\mu\text{g}/\text{m}^2$. Although the pilot study showed promising results in the FARS assessment, the lack of clinically meaningful effects on other outcomes indicate a higher dose may be necessary in the treatment of FA. During the ACTIMMUNE development program, the 100 $\mu\text{g}/\text{m}^2$ dose was administered to healthy adult subjects in PK studies, and doses $>100 \mu\text{g}/\text{m}^2$ were administered to subjects with disease states other than the approved indications. As expected, the AE profile of ACTIMMUNE at $>100 \mu\text{g}/\text{m}^2$ in other disease states was broader than that seen among patients with CGD at the 50 $\mu\text{g}/\text{m}^2$ dose. Since the safety profile of the 100 $\mu\text{g}/\text{m}^2$ dose is unknown among pediatric subjects with FA, the study will be monitored by a DSMB, which will advise the Sponsor or its delegate regarding the continuing safety of study subjects and potential subjects as well as the continuing validity and scientific merit of the trial. The decision to modify or halt the study will be made collectively by the CPI, the Sponsor (Horizon), and FARA after review with the FDA.

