2. STUDY OBJECTIVES AND ENDPOINTS

2.1 Study Objectives

2.1.1 Primary Objective

The primary objectives of this study are:

- To evaluate the long-term safety of ACTIMMUNE in subjects with Friedreich's Ataxia (FA).
- To evaluate the effect of ACTIMMUNE (interferon [IFN]- γ 1b) on the change from Baseline of HZNP-ACT-302 to Week 26 for all subjects and from Baseline of HZNP-ACT-301 to Week 26 of HZNP-ACT-302 (52-week treatment duration) for subjects receiving active treatment in both studies in neurological outcomes as measured by Friedreich's Ataxia Rating Scale (FARS) excluding the peripheral nervous system subscale score and the facial and tongue atrophy and fasciculations from the bulbar subscale score (FARS-mNeuro score).

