6.3 Derived and Computed Variables

The following derived and computed variables have been initially identified as important for the analyses of Safety, Efficacy and Exploratory endpoints. It is expected that additional variables may be required. The SAP will not be amended for additional variables that are not related to the primary target or key secondary target variables. Any additional derived or computed variables will be identified and documented in the SAS programs that create the analysis files. If the SAP is not amended, further derivations related to primary and secondary target variables will be described in the CSR.

- 302 Baseline = The last non-missing measurement/assessment on the date of Week 26 Visit from HZNP-ACT-301. If this measurement is missing or otherwise unavailable, it will be the last non-missing measurement/assessment on or prior to first dose in HZNP-

ACT-302.

- 301 Baseline = The last non-missing measurement/assessment prior to first dose of Study in HZNP-ACT-301.
- Study Day = Assessment Date – Date of Enrollment + 1
- Change from Baseline = Value at Post-Baseline – Value at Baseline
- Concomitant Medication is defined as any medication a subject has received concurrently with study treatment.
- Prior Medication is defined as any medication or therapies initiated prior to date of first dose of study drug. Medications that are started prior to the date of first dose of study drug and continue after the first dose of drug are considered to be both prior and concomitant medications.
- Treatment-Emergent Adverse Event (TEAE) – A TEAE is any adverse change from the subject's baseline condition that occurs on or after the date of the first dose of study drug through the duration of the clinical study.
- Related TEAE – Any TEAE with a reported relationship to study drug of 'possibly related'.
- Compliance = Calculated as the percentage of the number of vials used divided by the expected number of vials used, where the number of vials used is the number of used vials returned.

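### The adverse event tables carry no time or dose dimension, so for any one term they cannot separate events confined to escalation from events that start or recur later

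*SAP*

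**What the plan says.** - **Objective.** Protocol Section 8.1: "The primary objective is to evaluate the long-term safety of ACTIMMUNE". SAP Section 2.1.1 repeats this objective, and SAP Sections 2.2, 8 and 10 remove all efficacy analysis, so safety is the whole content of the report.
- **What is unknown.** Protocol Section 9.2 says that the safety profile of the 100 µg/m² "dose is unknown among pediatric subjects with FA, the study will be monitored by a DSMB".
- **Event window.** Under SAP Section 6.3 a treatment-emergent event is one that "occurs on or after the date of the first dose of study drug through the duration of the clinical study". Protocol Section 9.5.3.1.2 ends that window at the Follow-Up Safety Visit, two weeks after the last dose.
- **Tabulation.** SAP Section 9.1: summaries of "individual TEAEs by MedDRA System Organ Class (SOC) and preferred term will be displayed by overall treatment received". The counting rule is "Each subject will be counted only once within each preferred term". For a repeated term, "only the TEAE with the strongest relationship or the maximum intensity, as appropriate, will be included in the summaries of relationship and intensity".
- **Exposure.** SAP Section 9.6 summarises exposure over the study as a whole and specifies no time at each dose level.
- **Dosing phases.** Protocol Sections 9.4.1 and 9.4.1.1 plan 10, 25, 50 and 100 µg/m² in successive weeks if tolerated, allow adjustment up to Week 13, and then hold a stable tolerated dose, which may be below 100 µg/m².

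**The concern.** The treatment period has distinct phases, and the protocol expects events to differ between them. Section 7.3 says "Natural tolerance to FLS develops relatively quickly in the majority of patients receiving IFNs", and Section 9.2 expects constitutional symptoms to ease as treatment goes on. A long-term safety report should let the reader see whether that happened.

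As planned, a fever in Week 1 at 10 µg/m² and a fever in Week 20 at 100 µg/m² enter the table identically, and a subject who has both adds one. The intensity table keeps that subject's worst episode without showing when it occurred. The reader of the summary tables cannot tell, for a given term, whether onset was confined to the escalation weeks, nor at what dose the events began.

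**Working it through.** The documents give no sample size basis and no expected event rate for this study, so there is no planned figure to reproduce. The check has four parts.

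**1. Which safety outputs have a time dimension (SAP Section 9)**

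| Data | Summarised by |
|---|---|
| Laboratory (9.2), immunogenicity (9.2.1), vital signs (9.3), ECG (9.4) | visit |
| Adverse events (9.1) | whole window |
| Exposure and compliance (9.6) | whole study |

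Adverse events lack the time axis that most other safety data have, and no person-time by dose level is specified that could serve as a denominator.

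**2. What a pooled cell can tell the reader**

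Take one preferred term and N subjects, and assume for simplicity that nobody leaves early. Let A be the subjects with an onset during escalation and B those with an onset afterwards. The planned cell is P = |A ∪ B| / N.

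- If all onsets fall in escalation, B is empty and P_B = 0.
- If every counted subject also has a later onset, P_B = P.
- So 0 ≤ P_B ≤ P for any reported P.

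Even if P_A were known, the bound would only narrow to P − P_A ≤ P_B ≤ P, because subjects with both are counted once. Counting once per term *per period* is what resolves it. The argument applies within a preferred term only: an early event under one term does not remove a later event under another.

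**3. How much of planned dosing is at each level**

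Inputs: two doses in the first week at 10 µg/m², then three a week, stepping to 25, 50 and 100 µg/m² on Days 8, 15 and 22, for 26 weeks in all. The Week 26 clinic dose is counted within the 26 weeks.

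- Total doses: 2 + 25 × 3 = 77.
- Below 100 µg/m²: 2 + 3 + 3 = 8, and 8/77 = 10.4%.
- At 100 µg/m²: 77 − 8 = 69, and 69/77 = 89.6%.
- Days 1–28: 2 + 3 + 3 + 3 = 11, and 11/77 = 14.3%. This includes three doses already at 100 µg/m².
- Cumulative planned dose below 100 µg/m²: 2×10 + 3×25 + 3×50 = 245 µg/m². At 100 µg/m²: 69 × 100 = 6,900. Share: 245/7,145 = 3.4%.

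The 90% holds only if escalation goes to plan. Adjustment may run to Day 92, so up to 92/183 = 50.3% of treatment days can precede the settled dose.

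**4. Length of the event window**

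The Week 26 visit is Day 183 and the follow-up visit Day 197. The window is 197/7 ≈ 28 weeks, of which 197 − 183 = 14 days (14/197 = 7.1%) are off drug and are merged with on-drug time.

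**The case against.** The case for leaving the plan alone has weight.

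- This is an uncontrolled extension reported in an abbreviated safety report, without inference (SAP Sections 2.2, 5.1 and 9.1). Crude incidence by system organ class and preferred term breaks no rule in either document. **This stands**, and it is why the point is an improvement and not an error.
- Every event appears in the listings, start and stop dates are collected (Protocol Section 10), and the SAP permits identified post-hoc analyses and separate updating of output shells (Sections 4.2 and 12). So no data are lost. But listings and by-visit laboratory tables do not supply event incidence by phase, and a split chosen after the data are seen is weaker than one stated beforehand.
- The planned table is already mostly exposure at 100 µg/m², by the 90% above. **This stands for the planned schedule.** It does not help for terms whose onsets cluster early, or for subjects who settle lower.
- A split by period does not isolate 100 µg/m²: the first four weeks contain all four levels, and later periods mix 100 µg/m² with lower stable doses. **Correct**, which is why dose at onset is a separate request.
- The list of planned tables in SAP Section 13 is not readable in the copy reviewed, so a table by onset cannot be excluded. The SAP text describes none.

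A reader might go further and infer that early flu-like events overwhelm the whole adverse event table, or hide later events of other kinds. The documents do not support that. Counting is per preferred term, so flu-like events fill only their own rows, and no rate by phase is given. The label's fever rate cannot supply one: it comes from a different disease, at 50 µg/m² and without titration. Nor is escalation imposed regardless of tolerability; each step depends on the previous dose being tolerated.

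**Conclusion.** The point holds in a limited form. Within any one preferred term, the tables described in SAP Section 9.1 cannot distinguish events confined to escalation from events that start or recur later, and they do not show dose at onset. The uncertainty is the full range from 0 to the reported incidence. How much this will matter in practice cannot be sized from the documents, because it depends on how far onsets cluster early.

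This rests on reading the SAP's overall-treatment grouping as a single pooled column, and on the unreadable table list adding nothing to the text. If columns by HZNP-ACT-301 treatment were restored, as the statistical section of the protocol synopsis requires, the lack of a time and dose split would remain. That discrepancy between protocol and SAP is a separate matter.

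The primary objective names no dose, so it would be too strong to say that the plan fails its objective. It is a cheap improvement that would let the report describe when events begin during treatment.

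**What to change.** Add to SAP Section 9.1:

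1. **By period of onset.** Treatment-emergent event incidence by system organ class and preferred term for: first home dose to Week 4; Week 4 to Week 13; Week 13 to last dose; and off-drug follow-up, shown separately. Use subjects on drug at the start of each on-drug period as the denominator, and count each subject once per term per period.
2. **By dose level at onset, where dosing records allow.** Event counts with person-weeks at each level, labelled descriptive. The condition is real: compliance in SAP Section 6.3 is based on vials, and the same vial serves different dose levels, so vial counts alone will not reconstruct dose.
3. **Dates.** Correct the cross-reference for imputing adverse event dates. Section 9.1 points to Section 6.1, which covers visit windows; partial dates are introduced in Section 6.2. An onset-period table depends on this rule.

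Cost: one or two extra tables, the first from start dates already collected, and no change to study conduct. Cells may be sparse, and dose level is confounded with time on drug, so the second table cannot support a dose-response claim. An event that begins in escalation and continues without a break will appear only in the first period; its duration must still be read from the stop dates in the listings.

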9.1.1 Deaths

A summary and data listing of deaths that occurred will be provided, displaying details of the event(s) captured on the CRF.

9.2 Clinical Laboratory Evaluations

Descriptive summaries of actual (absolute) values and changes from baseline will be presented for Chemistry, Urinalysis, Complete Blood Count, PR, INR, and aPTT. These tables will be grouped by visit, and overall treatment.

The number and proportion of subjects with clinical laboratory values below, within, or above normal ranges, at each study visit will be tabulated (shift tables) for each clinical laboratory analyte by treatment group. Normal ranges will be provided by the central laboratory (URMC) used in this study.

Laboratory values will be displayed in data listings and those that are outside the normal range will be flagged, along with the corresponding normal ranges.

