5.3 Bone Marrow Toxicity

Reversible neutropenia and thrombocytopenia that can be severe and may be dose related have been observed during ACTIMMUNE therapy. Monitor neutrophil and platelet counts in patients with myelosuppression during treatment with ACTIMMUNE.

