5.4 Hepatic Toxicity

Repeated administration of ACTIMMUNE to patients with advanced hepatic disease may result in accumulation of interferon gamma-1b. Frequent assessment of liver function in these patients is recommended.

Elevations of aspartate transaminase (AST) and /or alanine transaminase (ALT) (up to 25-fold) have been observed during ACTIMMUNE therapy. The incidence appeared to be higher in patients less than 1 year of age compared to older children. The transaminase elevations were reversible with reduction in dosage or interruption of ACTIMMUNE treatment. Patients begun on ACTIMMUNE before age one year should receive monthly assessments of liver function. If severe hepatic enzyme elevations develop, ACTIMMUNE dosage should be modified [see *Dosage and Administration (2.3)*].

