2.2.1 Safety Endpoints

Adverse event and concomitant medication data will be summarized. Clinical laboratory safety data, vital sign data, echocardiogram data, and ECG interval data will be summarized with descriptive statistics for Baseline of HZNP-ACT-302, post-dose, and change from Baseline of HZNP-ACT-302 to post-dose values. Shift tables will be presented for clinical laboratory values and ECG categorical results from Baseline of HZNP-ACT-302 to each post-dose visit. Physical examination findings will be listed by subject. Results of immunogenicity testing will be presented in tabular format.

[figure not shown]

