- ¹ On Day 1 (Baseline), subjects will receive the last dose of assigned study drug (ACTIMMUNE or placebo) for HZNP-ACT-301, and undergo assessments; these assessments will serve as the Week 26 assessments for HZNP-ACT-301 and the Baseline assessments for HZNP-ACT-302.
- ² Height and weight will be measured at Baseline/Day 1 (Week 26 of Study HZNP-ACT-301), and Weeks 4, 13, and 26 to determine BSA; dosing will be based on BSA at Baseline/Day1, and Weeks 4 and 13.
- ³ Study drug will be initiated at home following the Baseline/Day 1 visit at 10 $\mu\text{g}/\text{m}^2$ according to the subject's TIW dosing schedule. The planned dose escalation consists of two doses of ACTIMMUNE 10 $\mu\text{g}/\text{m}^2$ in the first week, followed by weekly escalation to 25, 50, and 100 $\mu\text{g}/\text{m}^2$ TIW on Days 8, 15, and 22, respectively; however, the dose may be reduced, interrupted, or held based on tolerability. All subjects are to be on a stable tolerated dose of study drug by Week 13 in order to continue study participation
- ⁴ At the Baseline/Day 1 visit (Week 26 of Study HZNP-ACT-301), subjects will receive the last dose of study drug from the double-blind Study HZNP-ACT-301 (ACTIMMUNE or placebo). The first dose for this open-label extension study (ACTIMMUNE 10 $\mu\text{g}/\text{m}^2$) will be administered at home before bedtime according to the subject's TIW dosing schedule. Dosing at Weeks 4, 13, and 26 will be performed at the clinic. All other doses will be administered at home before bedtime.
- ⁵ Subjects will be given a 4-week supply of study drug prior to clinic discharge at the Baseline/Day 1 Visit (Week 26 of Study HZNP-ACT-301). At the Week 4 and 13 Visits, subjects will be given a 6-week supply of study drug, and additional study drug will be directly shipped to the subjects' homes as needed; if direct shipment is not feasible, subjects may receive a full supply at Weeks 4 and 13 (9-week supply at Week 4 and 13-week supply at Week 13).
- ⁶ Subjects and/or caregivers will be contacted by email or phone to monitor safety and dosing logistics on a weekly basis during the dose-escalation period (from Day 1 through at least Week 4 [or later until a stable tolerated dose is reached]) and on a monthly basis after dose stabilization (from Week 4 or when dose is stabilized) through Week 26.
- ⁷ Functional staging, FARS, T25W, and 9-HPT will be performed at approximately the same time of day at each visit and by the same examiner.

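### SAP 9.2 sorts laboratory values only as below, within or above normal, so no described table counts subjects by the size of a transaminase rise or a cytopenia

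*SAP*

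**What the plan says.** SAP 9.2 plans two kinds of laboratory table. The first is a by-visit summary of actual values and changes from baseline. Under SAP 6 this gives n, mean, SD, median, minimum and maximum. The second is categorical: the number and proportion of "subjects with clinical laboratory values below, within, or above normal ranges, at each study visit will be tabulated (shift tables"). The reference is the laboratory's own range: "Normal ranges will be provided by the central laboratory (URMC) used in this study". No ULN multiple, toxicity grade or marked-abnormality criterion is defined.

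SAP 2.2.1 fixes the starting point: "Shift tables will be presented for clinical laboratory values and ECG categorical results from Baseline of HZNP-ACT-302 to each post-dose visit". SAP 6.3 defines it: "302 Baseline = The last non-missing measurement/assessment on the date of Week 26 Visit from HZNP-ACT-301". At that visit, according to the footnotes to the SAP schedule of events, "subjects will receive the last dose of assigned study drug (ACTIMMUNE or placebo) for HZNP-ACT-301, and undergo assessments".

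Three further rules bear on the point. SAP 9.2 lists all values and flags those out of range. SAP 6 lists results from unscheduled visits but does not summarize them. SAP 6.2 ignores a repeat test unless the original is missing or invalid.

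**The concern.** SAP 2.2, 8 and 10 remove every efficacy analysis and reduce the output to an abbreviated safety report, so the safety tables carry the study. Protocol 9.2 describes the safety profile of the 100 µg/m² dose in pediatric FA subjects as unknown. Protocol 9.1 and 9.4.1.1 use raised liver function tests as their example of a drug-related event that may lead to dose reduction. The label reproduced in Protocol 17.2 (label section 5.3) adds: "Reversible neutropenia and thrombocytopenia that can be severe and may be dose related have been observed during ACTIMMUNE therapy".

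A reader of the report will want to know how many subjects had a marked transaminase rise or a marked fall in neutrophils or platelets. A table with a single high category and a single low category cannot say. It also cannot register worsening in a subject who starts outside the range. That is a particular worry where Baseline follows 26 weeks of the same drug.

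**Working it through.** The plan states no figure to reproduce. The check applies its classification rule to illustrative values, scaled so that ULN = 1.

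**Inputs.** Three categories and the laboratory's normal range (SAP 9.2); shift from 302 Baseline (SAP 2.2.1, 6.3); summary statistics (SAP 6); laboratory visits at Days 29, 92 and 183 (Protocol 2.1). The documents give no N, so N = 20, 40 and 90 are assumptions.

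**1. Same cell.** The rule is *above* if value/ULN > 1. Values of 1.1, 2, 5, 10 and 20 x ULN are all *above*.

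**2. Already high at Baseline.** A move from 1.5 to 20 x ULN goes from *above* to *above*, which is no shift. The change is 20 − 1.5 = +18.5 x ULN, which would appear in the maximum of the change-from-baseline summary. By the same rule, a neutrophil or platelet count already below range that falls further stays *below*.

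**3. One extreme subject.** Put one subject at 20 x ULN and the rest at 0.5, then replace the 20 by 1.1.

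| N | Mean with 20 x ULN | Mean with 1.1 x ULN | Median (both) | Count *above* (both) |
|---|---|---|---|---|
| 20 | (19×0.5 + 20)/20 = 1.48 | (9.5 + 1.1)/20 = 0.53 | 0.50 | 1 |
| 90 | (89×0.5 + 20)/90 = 0.72 | (44.5 + 1.1)/90 = 0.51 | 0.50 | 1 |

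The maximum separates the two cases (20 against 1.1). The shift table does not.

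**4. One extreme subject against five.** Take N = 40 with 30 subjects at 0.5.
- Case A: nine at 1.1 and one at 20. Mean = (15 + 9.9 + 20)/40 = 1.12.
- Case B: five at 1.1 and five at 20. Mean = (15 + 5.5 + 100)/40 = 3.01.

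Both give 10 *above*, median 0.50, minimum 0.5 and maximum 20. The mean and SD differ, but neither converts to a number of subjects. The count over 5 x ULN is 1 in A and 5 in B, and only the listing would show it.

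**5. Results between visits.** The on-treatment laboratory visits are 92 − 29 = 63 and 183 − 92 = 91 days apart. Protocol 9.5.3.7 asks for additional samples when clinically indicated. Protocol 9.5.3.1.6 asks for immediate repeats of unexplained significant abnormalities. Under SAP 6 and 6.2, a peak caught at an unscheduled visit, or in a repeat of a valid sample, is listed but enters no laboratory table.

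**The case against.** The best defence is that the three-category table does not stand alone. The maximum and the change-from-baseline maximum would reveal a single extreme, including worsening from a high Baseline; the minimum does the same for cell counts. Listings flag out-of-range values beside the normal range, and with about four centers they might be counted by hand. Protocol 9.5.3.1.1 makes any laboratory abnormality judged clinically significant an adverse event, Protocol 9.5.3.1.3 grades it, and SAP 9.1 counts subjects by preferred term and maximum severity. The protocol promised only descriptive statistics and shift tables, and the SAP delivers both. The list of planned tables in SAP 13 is not legible in the public copy, and SAP 12 allows shells to be updated separately, so a suitable table cannot be ruled out.

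Most of this stands. A reader might infer that severe laboratory toxicity would go unseen; the documents do not support that. What the defence does not supply is a count by numeric threshold. Steps 3 and 4 show the limit of the summary statistics. The listing flag uses the same normal-range cut-off as the table. The adverse event grades rest on tolerability, function and need for treatment, carry no laboratory cut-offs, and apply only to results the investigator judges significant.

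**Conclusion.** The point holds as a cheap improvement, not as an error or a contradiction of the protocol. Within the high or the low category the shift table has no sensitivity to size or to further worsening, and no table in the readable SAP text fills that gap. The working values are illustrative, and the number of subjects affected is unknown.

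Two stronger readings should be avoided. First, the label's transaminase elevations of up to 25-fold (label section 5.4) invite the claim that a 1.1-fold and a 25-fold rise are tabulated alike. Label section 6.2, where the 25-fold figure is explained, gives it as a rise from baseline in patients treated before age one year. Subjects here were 10 to 25 years old at the start of HZNP-ACT-301 (Protocol Table 7.1). As a rise from baseline the claim is also generally false: a 1.1-fold rise crosses the ULN only from a baseline above 1/1.1 = 0.91 x ULN. From 0.5 x ULN, 1.1-fold gives 0.55 (*within*) and 25-fold gives 12.5 (*above*), which are different cells. The figure is not a measure of the gap. Second, the on-drug Baseline applies only to subjects given ACTIMMUNE in 301, not to the former placebo group, and the documents do not say how many enter with abnormal values.

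**What to change.** In SAP 9.2, add the number and percentage of subjects by worst post-baseline value, including unscheduled and repeat results, among subjects with at least one post-baseline value. Show this by 302 Baseline category and by treatment received in HZNP-ACT-301. The protocol synopsis already calls for summaries by 301 treatment as well as overall. Either of two schemes would do, fixed before database lock:

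- **Thresholds.** ALT or AST above, for example, 3, 5 and 10 x ULN, and ALT or AST above 3 x ULN with total bilirubin above 2 x ULN. Add graded neutrophil and platelet cut-offs, for example below 1.5, 1.0 and 0.5, and below 100, 75 and 50, x10⁹/L respectively.
- **Grades.** One named toxicity grading scale, with grade-to-grade shifts from Baseline.

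These cut-offs are proposals; none comes from the documents. Protocol 9.5.3.7 does not itemize the chemistry panel, so the bilirubin row depends on bilirubin being in it. SAP 6 and 6.2 need a stated exception so that unscheduled and repeat results can enter this table.

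The categories are for reporting only and change no dosing or stopping rule. The cost is one or two tables from central laboratory values and ranges already planned for collection, and a safety summary that may look less favourable.
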